1.0 OBJECTIVES AND STUDY ENDPOINTS

Primary endpoint

1. Determine the overall response rate (complete remission plus partial remission) in Richter transformation (RT) after 2 courses of blinatumomab, ibrutinib and nivolumab treatment.

Secondary endpoints

1. Assess the safety and feasibility of administering blinatumomab combined with ibrutinib and nivolumab to patients with RT.
2. Determine the complete remission rate for RT after 1 and 2 courses of therapy.
3. Determine the progression-free survival rate for RT at 1 year.
4. Determine the overall survival rate for RT at 1 year.
5. Determine the proportion of patients who proceed to allogeneic stem cell transplantation as next treatment.

Exploratory objectives

1. Pre- and post-treatment (progression) tumor biopsies for immunologic analysis, including immune checkpoint expression by tumor and by infiltrating T cells, flow cytometry and RNA-sequencing analysis (including the potential to perform single cell RNA-seq) or array-based analysis of immune cell subsets.
1. Immune checkpoint expression by circulating T cells and T cell subset analysis.
2. “Liquid biopsy” using circulating tumor DNA analysis and comparison with mutational profile identified in concurrent CLL specimen and tumor biopsy. This will also be used as an MRD analysis tool.

Correlation of RT microRNA profile with response to treatment and outcomes.

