4.4 Response assessment

Formal response assessment will take place 2weeks (+/- 1 week) following completion of the first course of blinatumomab.. Response assessment will comprise laboratory evaluation (CBC), bone marrow examination and PETCT scan. Responses in RT for the primary study endpoint will be assessed according to the Lugano criteria¹⁹ and, as an exploratory endpoint, in co-existing CLL, according to 2018 IWCLL response criteria. Responses in RT will be assessed separately from responses in CLL. Any nodal or extranodal lesion with SUV ≥ 5.0 on PETCT will be considered indicative of RT, for the purposes of response assessment. Lesions with SUV <5.0 pre-treatment will be considered to be due to CLL, rather than RT; residual PET avidity in such lesions post-treatment will not be considered evidence of failure of control of RT, provided SUV remains <5.0 . In order for CR to be attained, all lesions with SUV ≥ 5.0 pre-treatment must be PET negative post-treatment and there must be no new PET avid lesions, unless these are proven by biopsy not to be due to Richter

Transformation. PET characterization of target lesions as due to CLL or RT pre-treatment will allow separate response assessment for RT (the primary end point) and CLL (an exploratory endpoint), without discrepancies arising due to the differences in response criteria. When possible, biopsy of residual RT sites will be requested to evaluate for residual disease.

Please note that there may be instances where PETCT is not able to be performed. In these instances, CT scan will be performed instead (see section 8.0 and 9.0)

A second response assessment will be undertaken 4 weeks (+/-1 week) after completion of the consolidation cycle.

4.5 Allogeneic stem cell transplantation.

In patients where a suitable donor is identified and who are considered eligible, allogeneic stem cell transplantation may be offered any time after completion of the first cycle of blinatumomab and initial response assessment. Patients will be considered “off study” on the date they commence pre-transplant conditioning chemotherapy. If the patient agrees, they will be enrolled on a departmental umbrella protocol (DR09-0223) to continue to follow them for overall survival.

4.6 Surveillance after completion of blinatumomab.

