After completing blinatumomab, patients will have PETCT every 3 months until completion of nivolumab therapy. If PETCT cannot be performed, for whatever reason, CT with oral and IV contrast (unless contraindicated) will be performed instead.

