9.0 EVALUATION DURING TREATMENT

Table 4: evaluation which will take place pre-treatment and during the study

Assessment	Base-line(1)	Cycle 1				Response assess	Cycle 2						Response assess	Ibrutinib + nivolumab consolidation (q4w for 36 weeks from 2 nd response assessment)	Surveillance (2)	At progression/ End-of-study
Day within cycle(3)	-28 to 1	1	15-31	36	43	57 (+/- 1 week)	1-3	8	15	22	29	43	57 (+/- 1 week)			
Informed consent(4)	X															
Medical history(5)	X	X	X	X	X	X	X	X	X	X	X	X	X	X	q12w	X
Physical examination(6)	X	X	X	X	X	X	X	X	X	X	X	X	X	X	q12w	X
Neurological examination(7)	X	X	X	X	X		X	X	X	X	X					
Concomitant medications(8)	X	X	X	X	X		X	X	X	X	X	X		X	q12w	X
CBC with differential(9)	X	X	X	X	X	X	X	X	X	X	X	X		X	q12w	X
Bio-chemistry(10)	X	X	X	X	X	X	X	X	X	X	X	X	X	X	q12w	X
Thyroid function(11)	X	q4 w														
Bone marrow(12)	X					X							X			X
PETCT scan(13)	X					X							X	q12 weeks	q24w	X
Lymph node biopsy(14)	X															X
Pregnancy test(15)	X															X
NGS panel(16)	X															X
Immunologic evaluation(17)	X															X
Tissue banking(18)	X															X
ctDNA(19)	X					X							X	At completion of nivolumab		X
Saliva (20)	X															

¹Baseline/screening testing. This must be performed within the timeframes outlined in table 3.

²Surveillance. Patients will have routine history and physical examination, CBC, routine biochemistry approximately every 12 weeks and a PETCT scan or CT scan with and without IV contrast approximately every 24 weeks (+/- 4 weeks) after completing ibrutinib + nivolumab consolidation, until 2 years after initiation of therapy, until relapse, allogeneic stem cell transplantation, or initiation of salvage therapy, whichever occurs first. Patients who have not proceeded to allogeneic

transplantation and who remain in remission at the end of the study, and those who proceed to transplant, will be enrolled on a departmental umbrella protocol (DR09-0223) to follow them for overall survival.

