It is expected that wherever possible, the clinical rather than laboratory term would be used by the reporting investigator (eg, anemia versus low hemoglobin value).

12.0 CRITERIA FOR REMOVAL FROM STUDY.

Criteria for removal from study include, but are not restricted to, the following:

- Clinically significant progressive disease.
- Recurrent non-compliance by the patient with protocol requirements.
- Patient's request to be removed from the study.
- Investigator's decision that a subject does not benefit from treatment anymore, e.g., non-response or development of progressive disease
- Transition to an alternative therapy, including allogeneic stem cell transplantation.
- Permanent cessation of nivolumab **and** blinatumomab: if a patient permanently discontinues either nivolumab or blinatumomab (but not both) due to adverse events, they may remain on study, if they continue to derive treatment benefit and benefit outweighs risk, in the opinion of the investigator. Patients who permanently discontinue both nivolumab and blinatumomab due to adverse events will be removed from the study.
- Permanent discontinuation of ibrutinib for any reason will not be an indication to remove a patient from study, if, in the opinion of the investigator, the patient is deriving benefit from treatment and it is safe to continue the other agent(s).

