14.0. STATISTICAL CONSIDERATIONS

The cohort of 9 patients already treated demonstrates the feasibility and safety of blinatumomab as a single agent for the treatment of RT. The overall toxicity profile of blinatumomab in RT was very favorable and this cohort of patients can be used as a “safety cohort,” prior to proceeding with a phase II study evaluating the combination with ibrutinib + nivolumab. As discussed above, the combination of ibrutinib and nivolumab was also very well tolerated.

We have completed a phase II study of ibrutinib + nivolumab, and achieved an ORR of 43%. This will serve as our “base case” estimation of the response rate that we would see with the combination of ibrutinib + nivolumab. If blinatumomab (ORR 1/8 = 12.5%) provides additive benefit only, this will result in an ORR of 50-55% with the combination of ibrutinib + nivolumab and blinatumomab. However, we expect synergy between the two regimens. We have therefore designed our statistical analysis around achieving an ORR of approximately 60%, which would suggest some synergy

between the two regimens. Higher response rates would suggest a greater degree of synergy between blinatumomab and ibrutinib + nivolumab, which we hope to achieve.

We propose to enroll an additional 21 patients, with the goal of evaluating the efficacy and safety of the proposed combination therapy. A sample size of 21 patients ensures that, if the trial is not terminated early, a posterior 90% credibility interval for overall response rate will have width of 0.33, under the assumption of a 60% of overall response rate (13/21 responses) and beta prior as described below. Under this scenario, the lower boundary of the 90% credibility interval matches the 43% ORR that was seen with ibrutinib + nivolumab therapy.

The primary outcome will be overall response (ORR), assessed after completion of 2 courses of blinatumomab.

We will utilize a Bayesian trial design to enable simultaneous monitoring of efficacy and toxicity using the approach of Thall, Simon, and Estey (1995, 1996). After an initial 6 patient safety cohort, subsequent patients will be enrolled in cohorts of size 3.

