	# Toxicities (inclusive)
3	Never stop with this many patients
6	4-6
9	5-9
12	7-12
15	8-15
18	10-18
21	Always stop with this many patients

Summary of operating characteristics

The operating characteristics are summarized in the table below. The probabilities of stopping the trial early are exact calculations from MultcLean Desktop under the assumption that response is independent of toxicity.

True Toxicity Rate	True OR Rate	Prob(stop the trial early)	Avg # patients enrolled (25 th – 75 th percentile)
0.2	0.6	0.04	20.5 (21 – 21)
	0.5	0.07	20.1 (21 – 21)
	0.4	0.19	19.0 (21 – 21)
	0.3	0.45	16.4 (12 – 21)
0.3	0.6	0.14	19.2 (21 – 21)
	0.5	0.17	18.8 (21 – 21)
	0.4	0.28	17.8 (15 – 21)
	0.3	0.51	15.5 (9 – 21)
0.4	0.6	0.36	16.4 (9 – 21)
	0.5	0.39	16.2 (9 – 21)
	0.4	0.46	15.4 (9 – 21)
	0.3	0.63	13.6 (6 – 21)
0.5	0.6	0.64	12.9 (6 – 21)
	0.5	0.66	12.7 (6 – 15)
	0.4	0.70	12.2 (6 – 21)
	0.3	0.79	11.1 (6 – 15)

Analysis Plan

Summary statistics will be provided for continuous variables. Frequency tables will be used to summarize categorical variables. Logistic regression will be utilized to assess the effect of patient prognostic factors on the response rate and the toxicity rate. The distribution of time-to-event endpoints will be estimated using the method of Kaplan and Meier. Cox proportional hazard regression will be employed for multivariate analysis on time-to-event outcomes.

An Efficacy/Safety Summary will be submitted to the IND Office Medical Monitor, after the first 6 evaluable patients complete 8 weeks of study treatment, and every 3 evaluable patients thereafter. Toxicity information of previously submitted patients will be updated during every submission.

Trial Conduct

Conducting a trial designed by this method does not require software since the stopping conditions have been tabulated before the trial begins.

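### Patients can leave follow-up before 1 year for reasons tied to prognosis, and the plan neither follows them for progression afterwards nor says how 1-year PFS treats them

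*Combined protocol and SAP*

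**What the plan says.** - **Endpoints (Section 1.0).** Secondary endpoint 3 is "Determine the progression-free survival rate for RT at 1 year". Endpoint 4 is the 1-year overall survival rate, and endpoint 5 is the proportion who go on to allogeneic transplant.
- **Analysis (Section 14.0, Analysis Plan).** "The distribution of time-to-event endpoints will be estimated using the method of Kaplan and Meier". No PFS event, time origin or censoring rule is given. The combination phase has 21 patients ("We propose to enroll an additional 21 patients").
- **Transplant (Section 4.5).** Transplant may be offered once the first blinatumomab course and the first response assessment are done. Patients are off study "on the date they commence pre-transplant conditioning chemotherapy". If they agree, an umbrella protocol then follows them for overall survival.
- **Removal (Section 12.0).** The investigator may remove a patient who "does not benefit from treatment anymore, e.g., non-response or development of progressive disease". Patients also leave for another therapy, or when nivolumab and blinatumomab have both been permanently stopped for adverse events. Stopping only one of those two, or ibrutinib, does not force removal.
- **Surveillance (Section 9.0, Table 4, footnote 2).** After consolidation, patients are assessed "until 2 years after initiation of therapy, until relapse, allogeneic stem cell transplantation, or initiation of salvage therapy, whichever occurs first". The umbrella protocol is to take patients still in remission at the end of the study and those who are transplanted.
- **Scans.** Section 4.6 says "patients will have PETCT every 3 months until completion of nivolumab therapy". Table 4 gives 12-weekly scans in a consolidation column that lasts 36 weeks from the second response assessment, 24-weekly scans after that, and a scan at progression or end of study.

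**The concern.** Kaplan-Meier is unbiased only if those censored have the same outlook as those still followed. The first-year exits in this plan are unlikely to meet that condition. A patient removed for non-response is probably close to progression. A patient sent to transplant will often have responded, and then receives a different treatment. The end-of-study scan fixes disease status on the day of exit and says nothing about month 12.

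The survival data have a gap too. The umbrella protocol names patients in remission and transplanted patients. It does not name those removed for non-response or starting salvage, so no survival follow-up is stated for them, although death is normally a PFS event and 1-year OS is an endpoint of its own. A trial run exactly as written would therefore not collect the data needed to say what happened to these patients by 1 year.

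**Working it through.** **1. Timeline against the plan's own figure.** Section 4.0 gives two 8-week cycles and nine 4-week cycles: 2 × 8 + 9 × 4 = 52 weeks. This reproduces the 52-week limit on nivolumab in Section 4.2.

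**2. Which exits fall before 1 year.** The first response assessment is on day 57 of cycle 1 (Table 4), about week 8, so transplant is possible from then. The removals in Section 12.0 can happen at any time. Sections 4.5 and 12.0 therefore carry the first-year problem. Footnote 2 covers the phase after consolidation, which on plan starts at week 52.

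**3. Scan calendar.** Twelve-weekly scans from the week-16 assessment fall at weeks 28, 40 and 52. The first 24-weekly scan is at week 76 (72 to 80 with the 4-week window). Planned thinning thus begins at the landmark. The exception is a patient who stops nivolumab early and stays on study. Read by Section 4.6, the 12-weekly scans end with nivolumab; if that happens by about week 16, scans fall at weeks 16, 40 and 64. Read by the Table 4 column, they continue to week 52. The two places disagree.

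**4. Range left open by unfollowed exits.** Exit counts are not in the documents, so *m* of 21 is an assumption. Counting all *m* as events and then all as progression-free moves the 1-year proportion by *m*/21:

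| *m* | *m*/21 |
|---|---|
| 2 | 0.095 |
| 4 | 0.190 |
| 6 | 0.286 |
| 8 | 0.381 |

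**5. Worked case (assumed counts).** Of 21 patients, 6 have early events, 4 then leave progression-free, and 4 of the remaining 11 have events by 1 year.
- Kaplan-Meier, censoring at exit: (15/21) × (7/11) = 0.455
- All four counted as events: 7/21 = 0.333
- All four progression-free at 1 year: 11/21 = 0.524

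**6. Direction of bias (assumed inputs).** Let S = 15/21 be progression-free at the time of exits. Of these, a fraction r is removed for non-response and a fraction t is transplanted. The chances of remaining progression-free to 1 year are a (removed), b (transplanted) and c = 0.6 (still followed). With censoring at exit, Kaplan-Meier tends to S × c = 0.429. The true value is S × [r·a + t·b + (1 − r − t)·c].
- r = 0.2, t = 0.1, a = 0, b = 0.6: 0.714 × 0.48 = 0.343, bias +0.086
- r = 0.1, t = 0.2, a = 0.2, b = 0.8: 0.714 × 0.60 = 0.429, bias 0
- r = 0.1, t = 0.2, a = 0.6, b = 1: 0.714 × 0.68 = 0.486, bias −0.057

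With 10% to 20% leaving by each route, the bias runs from about −0.06 to +0.09 over the values tried. Its sign depends on who leaves.

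**The case against.** The strongest reply is that PFS here is descriptive. It has no hypothesis, precision target or decision rule, and sizing and stopping rest on response and toxicity. With 21 patients the sampling error is already large: at 0.455, √(0.455 × 0.545 / 21) ≈ 0.11, ignoring censoring. Moderate bias would lie within that. This is fair and limits the weight of the point. It does not remove it, because sampling error is reported with the estimate and this uncertainty would not be.

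Several stronger readings are tempting, and the documents do not support them.
- *The estimate is informatively censored.* No passage says these patients are censored. Exits could be counted as events or handled as competing risks, though each answers a different question. The fault is that no rule is written.
- *PFS is biased upward.* Step 6 shows either sign. Transplant also depends on donor and eligibility, so transplanted patients cannot be assumed to be the best responders.
- *Thinner scans after nivolumab distort 1-year PFS.* On plan the thinning starts at week 52. It can matter only for early nivolumab stoppers who remain on study, and for them the text is ambiguous. Clinical visits and a scan at progression are also scheduled.
- *Any toxicity stop ends follow-up.* Removal requires both nivolumab and blinatumomab to be stopped.
- *The damage cannot be repaired.* Scans not done cannot be recovered, but analysis rules and bounds can be set before analysis, and records review can supply many dates if planned and permitted.

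Deaths after exit are also partly covered: Section 11.2 captures serious adverse events, which include death, to 100 days (about 14 weeks) after the last dose. For a patient whose last dose is between weeks 8 and 16, that reaches only about weeks 22 to 30.

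**Conclusion.** The point holds in limited form. One-year PFS and OS are named endpoints, several routes out of the study open well before 1 year, those routes are plausibly prognostic, and the plan states no progression follow-up after any of them. For removal through non-response or salvage it states no survival follow-up either. If these patients are censored at exit, 1-year PFS can be wrong in either direction. If 2 to 8 of 21 leave progression-free before 1 year, the best-to-worst-case range is 10 to 38 percentage points. That range rests on assumed exit counts, and the bias figures on assumed outcomes after exit.

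The primary response endpoint and the stopping rules are outside this point. It is an inexpensive improvement to secondary endpoints, not a flaw in the main design. Some front-matter and background text, and the umbrella protocol itself, could not be checked.

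**What to change.** - In Sections 4.5 and 12.0 and in Table 4 footnote 2, separate coming off treatment from coming off follow-up.
- For every treated patient, collect the date of RT progression, the date and type of next therapy, and the date of death or last contact, to at least 12 months from cycle 1 day 1. Records review under this protocol or the umbrella protocol would suffice.
- In Section 14.0, define the PFS event and time origin, and state before analysis how transplant, new therapy and off-study exit are treated. Report the alternative handling (such as censoring at transplant) and best/worst-case bounds as sensitivity analyses. Which handling of transplant is primary is a choice of question that the sponsor should make openly.
- Reconcile Section 4.6 with the Table 4 consolidation column for patients who stop nivolumab early but stay on study.

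The cost is protocol and consent wording plus chart follow-up for at most 21 patients. The drawback is that progression after exit would be read from routine-care scans rather than a fixed calendar, so those dates will be less exact.

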10.0 CRITERIA FOR RESPONSE

10.1 Richter's Transformation

Response assessment in RT will be performed according to the Lugano criteria for diffuse large B-cell lymphoma, as outlined in Appendix H.

10.2 Response Criteria in Chronic Lymphocytic Leukemia

The response of the co-existing CLL will be assessed according to the 2018 IWCLL criteria, which are re-produced in appendix I Overall response is defined as a CR or PR. Patients with missing or no response assessment will be classified as non-responders. The full criteria are re-produced below. The co-existence of RT may result in difficulty determining whether residual nodal, splenic or hepatic enlargement is due to persistent RT or CLL. For the purposes of response assessment, PET criteria

will be used to distinguish the two. However, if diagnostic difficulty exists, biopsy may be required.

11.0 ADVERSE EVENT REPORTING

Toxicities will be graded according to the NCI Expanded Common Toxicity Criteria.²¹

11.1 Leukemia-specific Adverse Event Recording and Reporting Guidelines

These guidelines serve to bring the Department of Leukemia in compliance with the institutional policy on Reporting of Serious Adverse Events.

An adverse event is any untoward medical occurrence that may present during treatment with a pharmaceutical product but which does not necessarily have a causal relationship with this treatment. An adverse drug reaction is a response to a drug which is noxious and unintended and which occurs at doses normally used in man for prophylaxis, diagnosis, or therapy of disease or for the modification of physiologic function.

Assessing causal connections between agents and disease is fundamental to the understanding of adverse drug reactions. In general, a drug may be considered a contributory cause of an adverse event if, had the drug not been administered, 1) the event would not have happened at all, 2) the event would have occurred later than it actually did, or 3) the event would have been less severe. The Investigator or physician designee is responsible for verifying and providing source documentation for all adverse events and assigning the attribution for each event for all patients enrolled on the trial.

11.1.1 Electronic case report (eCRF)

PDMS/CORe will be used as the electronic case report form for this protocol. Adverse events will be documented in the medical record and entered into PDMS/CORe.

11.1.2 Guidelines for recording and reporting of adverse and serious adverse events

These guidelines will be followed for the recording and reporting of adverse (AEs) and serious adverse events (SAEs).

1. Baseline events will be recorded in the medical history section of the case report form and will include the terminology event name, grade, and start date of the event. The medical history

section of the case report form will serve as the source document for baseline events once signed and dated by the principal investigator.

- a. Baseline events are any medical condition, symptom, or clinically significant lab abnormality present before initiation of treatment:
 - i. Hematologic laboratory abnormalities will not be recorded as baseline events for patients with acute leukemia, myelodysplastic syndrome, chronic lymphocytic leukemia, or chronic myeloid leukemia in blast phase.
 - ii. If exact start date is unknown, month and year or year may be used as the start date of the baseline event.
2. The maximum grade of the adverse event will be captured per course or protocol defined visit date.
3. These adverse events will be recorded in the case report form:
 - a. Any grade adverse event that is possibly, probably, or definitely related to the study drug(s).
 - b. All serious adverse events regardless of attribution to the study drug(s).
 - c. Any grade adverse event regardless of attribution to the study drug(s) that results in any dose modification.
 - a. Hematologic adverse events will be recorded and reported according to IWCLL guidelines, as outlined in Appendix J.
4. Serious adverse events will be reported according to institutional policy.
5. Protocol specific language regarding the recording and reporting of adverse and serious adverse events will be followed in the event of discordance between the protocol and Leukemia-specific adverse event recording and reporting guidelines.

